At day 7, if live lice are still present, a repeat treatment will be administered. After day 7 if a subject reports clear signs of infestation (i.e., the presence of live lice), they will be regarded as a treatment failure and they will be offered treatment with an alternative product (viz., Vamousse Mousse) by clinical staff.

For the treatment group, Clinical staff will apply Vamousse Spray 'n' Go to fully coat dry hair and scalp, avoiding the eyes and mucus membranes. The Treatment will be left on the hair and scalp for 8 hours, then standard at home shampoo and rinsed off with warm water, followed by combing. The Treatment spray bottle is intended for a single use although it contains a sufficient quantity for two treatments. All household members will be instructed on an overall lice management program, which includes:

- Wash (in hot water) or dry-clean all recently worn clothing, hats, used bedding and towels.
- Wash (in hot water) personal care items such as combs, brushes and hair clips.
- Record time and date product shampoo/rinse 8 hours post treatment

For the control group, Clinical staff will first shampoo the hair and scalp using regular shampoo. They will then

thoroughly rinse and towel dry the hair and scalp, and allow hair to air dry for a few minutes. Shaking the permethrin lotion well before applying, they will proceed to thoroughly wet the hair and scalp with the permethrin lotion, being sure also to cover the areas behind the ears and on the back of the neck. After allowing the lotion to remain in place for 10 minutes, they will then rinse the hair and scalp thoroughly and dry with a clean towel.

The site will provide Subject with lice management instructions. Subjects will return for post-baseline visits assessments at Day 2, Day 7, and Day 14.

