5.1 Inclusion criteria

1. Subjects must have an active head lice infestation defined as: At least 1 live lice (adults and/or nymphs) present on the scalp and/or hair, as determined by a trained evaluator.
2. Subjects must be at least two (2) years of age through 75 years of age, presenting with an active head lice infestation.
3. Subject is male or female.
4. Subject is at least 2 through 75 years of age at time of enrollment.
5. Subject is in good general health based on medical history.
6. Each subject must have an appropriately signed Informed Consent agreement. A caregiver must sign an Informed Consent agreement for children not old enough to do so. Children 6-17 years of age will be administered a child's Assent Form.
7. The caregiver of a subject must be willing to allow all household members to be screened for head lice. If other household members are found to have an active head lice infestation, they must be willing and able to participate in receiving study product or Standard of Care.
8. Subject agrees not to use any other form of lice treatments (commercial, community-anecdotal, or mechanical/manual) while participating in the study.

8. Following application of the test product, subject agrees not to shampoo, wash, or rinse their hair or scalp until 8-hour post-treatment time has been reached and documented.
9. Subject agrees to not cut or chemically treat their hair while participating in the study.
10. Subject agrees to follow all study instructions, including attending all follow-up appointments.
11. Female subjects of childbearing potential must be willing to have a urine pregnancy test prior to inclusion in this study.

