6.1.5 Dosing and administration

Lice and nit removal is not performed prior to nor during dosing and administration. For the study drug (Vamousse Spray 'n' Go), separate hair into 3-4 sections with clips. Part hair in 1-inch sections, spray treatment to completely saturate each section. Work through hair with a comb to ensure full coverage down to the scalp. Pay special attention to the nape of the neck and behind ears. Thoroughly saturate all hair and scalp. To be effective, all lice and nits must come in contact with the product. Allow hair to dry naturally. Leave treatment in for a minimum of 8 hours. Avoid contact with eyes. Do not swallow. Thoroughly wash hands after applying study product. Vamousse Spray 'n' Go should be used in the context of an overall lice management program:

- Wash (in hot water) or dry-clean all recently worn clothing, hats, used bedding and towels.
- Wash (in hot water) personal care items such as combs, brushes and hair clips.

For the control drug (Nix Creme Rinse Lice Treatment), first shampoo the hair and scalp using regular shampoo. Then thoroughly rinse and towel dry the hair and scalp, and allow hair to air dry for a few minutes. Shaking the permethrin lotion well before applying, proceed to thoroughly wet the hair and scalp with the permethrin lotion, being sure also to cover the areas behind the ears and on the back of the neck. After allowing the lotion to remain in place for 10 minutes, rinse the hair and scalp thoroughly and dry with a clean towel.

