6.1.8 Tracking of at home compliance

Subject Home Instructions will be distributed and accounted for. Subjects will fill out their Subject Home Instructions noting the following:

- Time and date of removal (washing off the study drug in 8 hours, followed by thorough combing)
- Confirmation that subject disinfected personal items; worn clothing, hats, used bedding and towels
- Confirmation Wash (in hot water) or dry-clean all recently worn clothing, hats, used bedding, towels including combs, brushes and hair clips.

Subjects will return their Subject Home Instructions to the clinical site for compliance review at Follow-up Day 2, Day 7, and Day 14. The Investigator will verify that the subject complied with disinfection regimen. Both the subject and the study staff will sign off on completed Subject Household Instructions. If the subject has missed the disinfection notation, this is considered a protocol deviation and must be reported.

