7.3 Study schedule

7.3.1 Screening/randomization

Screening Visit Day 0 (Visit 1)

- Obtain informed consent of potential participant verified by signature on written informed consent.
- Record demographic information, obtain medical history, and history of head lice.
- Review medications history and concomitant/prohibited medications to determine eligibility
- Verify inclusion/exclusion criteria.
- Collect urine sample for pregnancy testing for all subjects of childbearing potential.
- Perform assessment for living head lice on subjects and household members for a minimum of 15 minutes. Each subject must have at least 1 live louse. Rate severity of infestation. After each subject has been identified, additional infested household members will also be assessed for infestation.
- Level of infestation will be rated as heavy, moderate or light described by how quickly lice were found during combing: heavy infestation = >1 louse with one stroke of the comb; moderate infestation = 1 louse with one stroke of the comb; light infestation = first louse found only after several strokes of the comb
- Household members must have an active head lice infestation defined as: At least 1 live lice (adult and/or nymph) present on the scalp and/or hair, as determined by a trained evaluator. Household members will be assigned to the same study group as index case.
- Schedule study visits for participants who are eligible and available for the duration of the study.
- Randomly assign subjects to treatment or control group based on infestation severity alternation system (i.e., randomly assign pairs of equal severity levels to treatment and control groups, a form of stratified random sampling) to achieve balanced representation of severity in the two groups.
- Investigational Product Dispensation/ Application for subject.
- Provide each subject with homecare instructions including combing after first wash out.
- Inform subject when to come back for each follow-up visit.
- Provide Standard of Care treatment on-site to unqualified infested household members.

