16.1 Schedule of events

Visit Number	Visit 1	Visit 2	Visit 3	Visit 4
Visit Day	Day 0	Day 2	Day 7	Day 14
Informed Consent	X			
Eligibility Criteria	X			
Subject Demographics	X			
Medical History	X	X	X	X
Physical Examination	X	X	X	X
Combing		X	X (if treatment needed)	
Investigational Product Dispensation	X		X (if necessary)	
Vital Signs	X	X	X	X
Urine Pregnancy Test	X	X	X	X
Head Lice Visual Assessment	X	X	X	X
Local Skin/Scalp Irritation Assessment	X	X	X	X
Ocular Irritation Assessment	X	X	X	X
Concomitant and Prohibited Medication Review	X	X	X	X
Adverse Events Assessment	X	X	X	X

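### Post-treatment combing is tied to the spray in the arm-specific text and to no arm elsewhere; unless this is reconciled and recorded, mechanical louse removal could differ between arms unnoticed

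*Combined protocol and SAP*

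**What the plan says.** **Arm-specific text**

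- Section 4.1, spray: 8 hours on the hair, "then standard at home shampoo and rinsed off with warm water, followed by combing".
- Section 4.1, control: after 10 minutes staff finish the procedure, and "they will then rinse the hair and scalp thoroughly and dry with a clean towel".
- Section 6.1.5, spray: at application, "Work through hair with a comb to ensure full coverage down to the scalp". The procedure stops at the minimum leave-in time and does not mention combing after wash-out.
- Section 6.1.5, control: "After allowing the lotion to remain in place for 10 minutes, rinse the hair and scalp thoroughly and dry with a clean towel". No combing at any step.
- Section 6.1.8, home compliance: subjects note the time of "washing off the study drug in 8 hours, followed by thorough combing". Only the spray has an 8-hour wash-off.

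**Text that names no arm**

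- Section 7.3.1: "Provide each subject with homecare instructions including combing after first wash out".
- Section 7.3.3: any repeat treatment at Day 7 is followed by thorough combing.
- Section 16.1: a Combing row marked at Day 2, and at Day 7 if treatment is needed.

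**Text that limits mechanical removal**

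- Section 5.1: "Subject agrees not to use any other form of lice treatments (commercial, community-anecdotal, or mechanical/manual".
- Synopsis, exclusion criterion 5: rules out physical or mechanical lice removal in any subject once lice have been diagnosed. It makes no exception for combing that the protocol itself directs.

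**The concern.** Section 2.1 names wet-combing among the effective ways to clear an infestation. The primary endpoint in 4.2.2 is freedom from live adults and nymphs at Day 14, so a louse combed out counts the same as a louse killed. The objective in section 3, however, concerns killing lice and eggs.

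A site working from 4.1 and 6.1.8 would comb the spray arm after wash-out and not the control arm. Any benefit of that combing would be credited to the spray. The trial is open label (2.2), so staff and families know which procedure applies. The home-instruction form (16.3) asks about the 8-hour wash and the laundry but not about combing, and the analysis sections (10.1, 10.4.2) do not mention it. If combing did differ between arms, the planned records would not show it and the planned analysis could not allow for it.

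**Working it through.** **1. Passages side by side**

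| Step | Spray | Control |
|---|---|---|
| Comb-through at application | Yes (6.1.5) | Not mentioned (4.1, 6.1.5) |
| Combing after wash-out, arm-specific text | Yes (4.1; 6.1.8 through the 8-hour wash) | Not mentioned (4.1, 6.1.5) |
| Combing after first wash-out, all subjects (7.3.1) | Clear: the home wash at 8 hours | Unclear: the product is rinsed off on site after 10 minutes |
| Day 2 combing (16.1) | Yes; purpose, tool and operator not stated | Same |
| Combing after Day 7 repeat treatment (7.3.3, 16.1) | Yes | Yes |
| Combing entry on the home form (16.3) | None | None |

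From Day 2 onward the text treats the arms alike. The gap lies at application and between application and Day 2. There the spray has explicit combing, and the control has only an instruction tied to an event that is not defined for it.

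**2. The plan's own sample size (10.5)**

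Inputs: 45% v 85%, two-sided alpha 0.05, power 0.80, allocation 1:1.

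Without continuity correction:

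n = [1.960·√(2·0.65·0.35) + 0.842·√(0.45·0.55 + 0.85·0.15)]² / 0.40² = 21.1, so 22 per group (44 in total).

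With continuity correction:

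n′ = (21.1/4)·[1 + √(1 + 4/(21.1·0.40))]² = 25.9, so 26 per group (52 in total).

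The stated 52 is reproduced with the correction, and 52/0.90 = 57.8 gives the stated 58 (29 per group).

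**3. Illustration of what unequal combing could do**

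The documents give no combing effect. Assume that the products are equally effective (45% lice free in each arm) and that combing adds c points in the spray arm only. The chance of a significant result favouring the spray is approximately

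Φ{[c − 1.960·√(2p̄(1−p̄)/n)] / √[(p₁(1−p₁) + p₂(1−p₂))/n]}, where p₁ = 0.45, p₂ = 0.45 + c and p̄ is their mean.

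- c = 0.10, n = 26: (0.10 − 0.2718)/0.1380 = −1.245, giving 10.7%.
- c = 0.20, n = 26: (0.20 − 0.2704)/0.1352 = −0.521, giving 30.1%.

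Exact binomial enumeration of the pooled Z test:

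| Assumed combing benefit, spray only | 26 per group | 29 per group |
|---|---|---|
| 0 points | 2.4% | 2.4% |
| +5 | 5.0% | 5.5% |
| +10 | 9.8% | 11.2% |
| +15 | 17.8% | 20.2% |
| +20 | 29.6% | 32.7% |

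These figures use the Z test throughout. Section 10.1 offers Fisher's exact test as one alternative when either group has fewer than 10 lice-free subjects. Repeating the enumeration with Fisher's test in those tables gives 1.5%, 7.6% and 27.0% at 26 per group for 0, +10 and +20 points: somewhat lower, with the same pattern.

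**The case against.** The strongest reply is that the protocol already combs everyone. Section 7.3.1 addresses each subject, 7.3.3 covers any repeat treatment and the 16.1 row names no arm. The control text is silent on combing, and silence is not a prohibition. The clause in 4.1 also has an ordinary explanation: the spray is washed off at home, so its home steps are described there, while staff rinse the control on site.

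Much of this stands. A reader might infer that the trial compares spray plus combing with permethrin alone. The documents do not support that, because the all-subject passages prescribe combing without excluding the control. A reader might also infer that the passages cannot all be followed. That too goes further than the text: 5.1 bars other forms of treatment, which can fairly be read as exempting combing that the protocol directs, and a site that combed every subject after wash-out would not contradict 4.1 or 6.1.5. Nor is 6.1.5 evidence of a difference in combing after wash-out, since it gives that step to neither arm. Section 6.1.8 is addressed to subjects generally and is tied to the spray only by the 8-hour wash.

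The illustration is open to challenge as well. It gives the control no combing benefit, whereas combing listed for both arms at Day 2, and after any Day 7 re-treatment, would tend to dilute an early difference by Day 14.

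What the reply does not settle is what a control subject is meant to do after an on-site rinse, why the comb-through at application appears for the spray only, and how instructed combing fits the synopsis exclusion. The Day 2 visit text (4.1, 7.3.2) does not mention combing, and 16.1 does not say whether that row means removal or detection; 4.2.3 refers to detection combing at Day 7.

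**Conclusion.** The point holds as a risk of unequal mechanical removal arising from unreconciled text. The arm-specific procedures attach combing to the spray, the all-subject instructions name no arm, and the link between them is undefined for the control. The documents do not show that the sponsor chose unequal combing.

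The size of any bias cannot be derived from the documents. The rise from about 2.5% to about 10% or 30% at 26 per group rests on three assumptions: equal product effect at the plan's 45% control rate, a benefit of 10 or 20 points that has no source in the documents, and no combing benefit at all in the control arm. It shows that a modest difference in combing could matter in a trial of this size. It does not estimate the trial's error rate.

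The matter should be settled because it bears on the primary comparison and, as planned, could not be detected afterwards.

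**What to change.** 1. Reconcile 4.1, 6.1.5, 6.1.8, 7.3.1, 7.3.3, 16.1 and the synopsis exclusion of mechanical removal, so that it is explicit whether post-treatment combing applies equally to both arms. State what the first wash-out means for the control, and whether the comb-through at application is meant for the spray only. The content of the instruction is for the sponsor to decide.
2. Add a combing entry to the home-instruction form (16.3) for both arms, and report combing by arm.
3. If combing is meant to differ by arm, word the conclusion as a comparison of regimens, not of the products' killing effect.

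The cost is protocol wording, one line on an existing form and one descriptive table. The sample size and the primary test do not change.

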4.2 Study outcome measures and endpoints

4.2.1 Outcome measures

Primary outcome measure: the proportion of subjects in a study group who are completely lice free, meaning no live adults or nymphs.

Secondary outcome measure: the decline in total number of live adult lice and nymphs from the baseline count.

4.2.2 Primary Endpoint

The proportions of participants in each of the study groups (i.e., treatment and control) who are completely free of live adult lice and nymphs at day 14

4.2.3 Secondary Endpoints

- Assessment of infestations detected: number of live adult and nymph forms at the 7-day visit confirmed by investigator inspection during detection combing.
- Proportion of subjects requiring re-treatment at 7 days.
- Proportion lice free at day 2 (i.e., 24 hours after first treatment)
- Volume of product used in relation to hair type (Volume will be weighted pre and post and weight will be recorded on the product log. Hair type will be recorded as fine, medium or coarse on source document.)
- Safety of the product – as determined by reported adverse events during the study and recalled at the end of the treatment period.
- Cosmetic acceptability of the product in daily use as determined by consumer assessment questionnaire at the 14-day visit.
- The mean change between day 14 and baseline in the counts of live lice (i.e., total of live adult lice and nymphs) in each study group (i.e., treatment and control).

5. Study Enrollment and Withdrawal

5.1 Inclusion criteria

1. Subjects must have an active head lice infestation defined as: At least 1 live lice (adults and/or nymphs) present on the scalp and/or hair, as determined by a trained evaluator.
2. Subjects must be at least two (2) years of age through 75 years of age, presenting with an active head lice infestation.
3. Subject is male or female.
4. Subject is at least 2 through 75 years of age at time of enrollment.
5. Subject is in good general health based on medical history.
6. Each subject must have an appropriately signed Informed Consent agreement. A caregiver must sign an Informed Consent agreement for children not old enough to do so. Children 6-17 years of age will be administered a child's Assent Form.
7. The caregiver of a subject must be willing to allow all household members to be screened for head lice. If other household members are found to have an active head lice infestation, they must be willing and able to participate in receiving study product or Standard of Care.
8. Subject agrees not to use any other form of lice treatments (commercial, community-anecdotal, or mechanical/manual) while participating in the study.

8. Following application of the test product, subject agrees not to shampoo, wash, or rinse their hair or scalp until 8-hour post-treatment time has been reached and documented.
9. Subject agrees to not cut or chemically treat their hair while participating in the study.
10. Subject agrees to follow all study instructions, including attending all follow-up appointments.
11. Female subjects of childbearing potential must be willing to have a urine pregnancy test prior to inclusion in this study.

5.2 Exclusion criteria

An individual who meets any of the following criteria will be excluded from participation in this study:

1. History of irritation or sensitivity to Vamousse Spray 'n' Go or the components, pediculicides or hair care products.
2. Presentation at the treatment site with visible skin/scalp condition(s) that are not attributable to head lice infestation, such as an erythema score that is >2, blisters, vesicles which, in the opinion of the investigative personnel or medical monitor, will interfere with safety and/or efficacy evaluations.
3. Presentation at the treatment site with eczema or atopic dermatitis.
4. Treatment for head lice (Over the counter [OTC], home remedy and/or Prescription) in the last 30 days.
5. Any condition or illness that, in the opinion of the investigator, may compromise the objective of the protocol.
6. Is receiving any other treatment which, in the opinion of the investigator or medical monitor, may interfere with the study results.
7. Females (including caregivers who come in contact with the investigational product) who are pregnant, nursing or planning a pregnancy which could include household subjects. If a household has a pregnant female who has an active case of lice, the entire household is excluded from participation and provided Standard of Care.
8. Household members of child-bearing potential, including subjects, and unwilling to use an adequate method of contraception for the duration of the study. Adequate methods of contraception include: abstinence, vasectomized partner, oral birth control pills, birth control injections or patches, Intra uterine devices, condoms with a spermicidal jelly or a diaphragm with spermicidal jelly, surgical sterilization. Subjects and/or caregivers will be considered non-child-bearing if the following has occurred: full hysterectomy or bilateral oophorectomy is considered surgically sterile. Tubal ligation is not considered equivalent to female sterilization.
9. Participation in a previous investigational drug study within the past 30 days.
10. Does not understand the requirements for study participation and/or may likely exhibit poor compliance, in the opinion of the investigator.
11. Does not have a known household affiliation with their household members (i.e., do not stay in one household consistently, sleeping at one place several nights and then at another place or location). Household is defined as living in a shared area or space (for example the same house or apartment unit).

5.3 Criteria for Inclusion of Minor Subjects

Subjects aged 6 years through 17 years of age must sign the Assent Form that will be written in such a way as to be understandable to a child and to obtain parental or legal guardian consent prior to enrollment in this study.

5.4 Strategies for recruitment and retention

- Expected total number of screened subjects will be 64.
- Given a 10% screen failure rate, an anticipated number of enrolled subjects will be 58.
- Assumed dropout rate is 10%, an expected number of 52 subjects will complete the study.
- Source of subjects will be primarily from established patient data base, community at large, area schools and daycares, along with referrals by local healthcare centers to research site.
- Retention of subjects will be supported by thorough visit reminders and proper education on the study itself, including study duration, activities and responsibilities.

